## ABBREVIATIONS

AE	Adverse Event
BCG	Bacille Calmette-Guerin
CCTU	Comprehensive Clinical Trials Unit
COVID-19	SARS-CoV-2-induced disease
DMC	Data Monitoring Committee
EC50	Half-maximum effective concentration
IC50	Half-maximum inhibitory concentration
IFN	Interferon
IL	Interleukin
ITT	Intention-To-Treat
MMR	Measles, Mumps and Rubella vaccine
NK	Natura Killer
OPV	Oral Polio Vaccine
OR	Odds Ratio
PCR	Polymerase Chain Reaction
RPMI	Roswell Park Memorial Institute
SAE	Serious Adverse Event
SARS-CoV-2	Virus causing COVID-19
SUSAR	Suspected Unexpected Serious Adverse Reaction
TNF	Tumor Necrosis Factor
TSC	Trial Steering Committee
UCL	University College London
WHO	World Health Organisation

## 1 INTRODUCTION

### 1.1 General principles of the Statistical Analysis Plan (SAP)

This document details the proposed analysis strategy for the sub-study of CROWN CORONATION, leading to scientific publication(s). The results reported in these papers will follow the strategy set out here, which adheres to the guidelines for the content of a statistical analysis plan. Moreover, the reporting of the main trial will adhere to the CONSORT guidelines.

Suggestions for subsequent analyses by oversight committees, journal editors or referees, will be considered carefully in line with the principles of this analysis plan. Subsequent analyses of a more exploratory nature will not be bound by this strategy, and will be detailed in separate analysis plans.

Any deviations from the SAP will be described and justified in the final reports. This document is intended to be stand-alone from the protocol and adhere to the main points in the analysis summary specified in the protocol. However, the SAP can undergo revision outside of the protocol.

### 1.2 Background and rationale of the sub-study

Adaptive memory immune responses (particularly B cells and antibodies) are considered the cornerstone of vaccination in humans. However, recent studies demonstrate that a memory-like response in innate immunity can also enhance resistance to infection. These observations have led to the paradigm-shifting concept of trained immunity, where functional reprogramming of innate immune cells such as monocytes, macrophages, and Natural Killer (NK) cells can improve immune responses against infections. Epidemiological studies have shown that certain vaccines employing live attenuated microorganisms such as Bacille Calmette-Guerin (BCG), measles-containing vaccines (such as MMR), and oral polio vaccine (OPV) exert heterologous protective effects against infections other than those for which these vaccines are administered, and this cannot be explained by induction of any specific T- or B cell responses. Vaccination with measles seems to induce a transient suppression of lymphoproliferative responses, but an increase in innate immune responses, as measured by nonspecific cytokine production.

Recent exposure to a vaccine may affect the immune response to subsequent vaccination with an unrelated vaccine. Such interaction between different vaccines has not been studied extensively. Evidence suggests that the chronological order of different vaccines in childhood immunization schedules can have a notable impact on overall childhood mortality. Interaction between vaccines may occur through modification of the adaptive response and / or modification of the innate immune response. Such interaction can be either positive or negative.

The rapid development and roll-out of specific SARS-CoV-2 mRNA vaccination in the USA,

coincided with enrolment of participants into the CROWN CORONATION trial (NCT04333732) – a study investigating the efficacy of the MMR vaccine to prevent symptomatic, PCR positive COVID-19. Subsequent to randomization to either MMR or placebo injection, a number of participants in the CROWN CORONATION trial were vaccinated with a SARS-CoV-2 mRNA vaccine.

### **1.3 Objectives of the sub-study**

The goal of this sub-study is to characterize and compare, in those exposed to a) recent MMR vaccination followed by SARS-CoV-2 vaccination and b) recent placebo injection followed by SARS-CoV-2 vaccination,

- I) the in-vitro, cytokine and chemokine responses (tumor necrosis factor (TNF)- $\alpha$ , interleukin (IL)-1 $\beta$ , IL-6, IL-10, IL-17, IL-22, interferon (IFN)- $\alpha$ , and IFN- $\gamma$ ) to heterologous stimuli.
- II) the SARS-CoV-2 neutralization assay (half-maximum effective concentration [EC50]; half-maximum inhibitory concentration [IC50]).

## 2 STUDY METHODS

### 2.1 Trial design

This is a sub-study within the CROWN CORONATION trial.

At Washington University in St Louis, consenting participants are recruited into the sub-study. Additional blood samples will be required from participants in the sub-study, to enable measurement of the outcomes of the sub-study. Apart from additional blood samples that will be collected from those in the sub-study, these participants will be treated the same as those taking part in the CROWN CORONATION trial.

### 2.2 Framework

CROWN CORONATION is a superiority trial. The aim is to demonstrate that the trial intervention(s) is(are) effective at decreasing the incidence of symptomatic COVID-19 disease.

In the sub-study, we hypothesize that, compared to SARS-CoV-2 mRNA vaccination alone, MMR vaccination prior to SARS-CoV-2 mRNA vaccination will induce lasting trained immunity in recipients, manifested by improved innate immune responses upon in vitro exposure of supernatants to heterologous pathogen products. We also hypothesize that MMR vaccination prior to SARS-CoV-2 mRNA vaccination does not alter the adaptive immune response to SARS-CoV-2 mRNA vaccination.

### 2.3 Randomisation

Sequence generation, allocation and implementation takes place within the CROWN CORONATION trial.

### 2.4 Sample size

All CROWN CORONATION participants who meet the inclusion criteria will be contacted for recruitment. We will enrol as many participants as possible into the sub-study. The eligible population size is 160.

For the purpose of sample size calculation, we used the t-test to compare the primary outcome between treatment arms, i.e. the difference in cytokine and IFN- $\gamma$  response between MMR and placebo groups. Table 1 reports power given the expected difference in IFN- $\gamma$  responses, with a two-sided type-1 error rate of 5%.

Table 1: Predicted power.

Stimulus	Expected difference between means (pg/ml)	Expected standard deviation	Power with 60 participants	Power with 100 participants	Power with 140 participants
TLR-3 ligand	400	900	39%	59%	74%
TLR-7/8 ligand	450	900	48%	70%	84%

## 2.5 Study outcomes

- i) Primary outcomes:
  - a. PBMC cytokine production (TNF- $\alpha$ , IL-1 $\beta$ , IL-6, and IFN- $\alpha$ ) 1 day after stimulation with heterologous products (inactivated SARS-CoV-2, live attenuated MMR viruses, toll-like receptor (TLR)-3 ligand, TLR-7/8 ligand, TLR-4 ligand, and RPMI medium).
  - b. IL-10, IL-17, IL-22, and IFN- $\gamma$  production 5 days after stimulation of PBMCs with heterologous products.
- ii) Secondary outcomes:
  - c. SARS-CoV-2 neutralization assay (EC50; IC50).
  - d. Measles IgG antibody titres

Timing: Blood collected at a single sub-study visit around 6 to 9 weeks following the participant's second SARS-CoV-2 mRNA vaccine injection.

### **3 STATISTICAL PRINCIPLES**

This sub-study is hypothesis generating. No adjustment will be made for multiple testing. All results comparing the treatment arms will be provided with 95% confidence interval (except if specified otherwise). Analysis will be for complete cases; no imputation will be performed for missing data. Missing data will be summarised and reported with results.

#### **3.1 Analysis population**

All randomised participant data will be included in the Intention-To-Treat (ITT) analysis according to the arm they were randomised to, irrespective of the actual study drug that they took. This ITT analysis will be the main strategy for the sub-study (primary and secondary outcomes).

A modified ITT analysis will be performed at the end of the CROWN CORNATION trial, based on serology results. Participants with evidence of COVID-19 infection at the start of the study will be removed from the analysis set. It is anticipated that this sub-study will be completed and reported on prior to analysis of the main trial so that the modified ITT analysis of the sub-study data will be reported separately.

#### **3.2 Baseline patient characteristics**

Baseline characteristics will be summarised for all participants in the sub-study. Summary measures for the baseline characteristics will be presented as mean and standard deviation for continuous (approximate) normally distributed variables, medians and interquartile ranges for non-normally distributed continuous variables, and frequencies and percentages for categorical variables. We will plot histograms of continuous variables to assess normality.

#### **3.3 Analysis methods**

The results of the analyses will be reported following the principle of the ICH E3 guidelines on the Structure and Content of Clinical Study Reports. There will be no imputations for missing data.

Endpoints will be summarised graphically with box-whisker-dot plots.

##### **3.3.1 Adjustment factors**

All models for the primary outcomes will be adjusted for sex and the calendar date of sample collection (by quarter of the year). Diagnostics for regression models will be assessed to ensure that underlying assumptions are met.

Sensitivity analyses will be performed by individually adding adjustment for age, interval duration between last SARS-CoV-2 vaccine injection and blood draw, interval duration between MMR or placebo injection and blood draw, and interval duration between MMR or

placebo injection and SARS-CoV-2 vaccination (figure 1). Outcomes will be plotted over time to assess the effect of the stated interval durations (figure 1) on the measured outcomes.

[figure not shown]

Figure 1: Interval durations in sub-study

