### 3.3.2 Primary endpoints analysis

TNF- $\alpha$ , IL-1 $\beta$ , IL-6, IL-10, IL-17, IL-22, IFN- $\alpha$  and IFN- $\gamma$  will be analysed by linear regression, with a coefficient for treatment arm, and adjusted for sex and the calendar date (which quarter of the year) of sample collection. The endpoints will be reported as the adjusted mean (95% CI) effect of MMR pre-exposure on the endpoint. For each specified endpoint, the individual participant assay response to RPMI will be evaluated and if the response is greater than three times the lower detectable limit of the assay, the data from that participant will be excluded from analysis for the specific endpoint. For example, if the IL-6 value is greater than three times the lower detectable limit in response to RPMI, the participant's data will be excluded from the analyses of IL-6 responses to the heterologous stimuli. The participant's data will still be used for the other endpoints in which the assay response to RPMI was less than three times the lower detectable limit.

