### 3.3.3 Secondary endpoints analysis

SARS-CoV-2 neutralization assay (EC50; IC50) and Measles IgG antibody titres will be analysed by linear regression, with a coefficient for treatment arm, and adjusted for sex and the calendar date (which quarter of the year) of sample collection.

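### Optional low-cost improvement: moving age from the sensitivity analysis into the main models can tighten the estimates if age explains more than about 1-2% of residual variance

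*SAP*

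**What the plan says.** SAP 3.3.2 fits each cytokine by linear regression "with a coefficient for treatment arm, and adjusted for sex and the calendar date (which quarter of the year) of sample collection". SAP 3.3.3 uses the same two covariates for the secondary endpoints: "SARS-CoV-2 neutralization assay (EC50; IC50) and Measles IgG antibody titres will be analysed by linear regression".

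Age appears only in SAP 3.3.1, among the sensitivity analyses: "Sensitivity analyses will be performed by individually adding adjustment for age, interval duration between last SARS-CoV-2 vaccine injection and blood draw". Two further intervals follow in that list, from MMR or placebo to blood draw and from MMR or placebo to SARS-CoV-2 vaccination. Each term is added on its own. No reason is given for keeping age out of the main model, and no age-outcome association is quoted.

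On the analysis set, SAP 3.1 states: "All randomised participant data will be included in the Intention-To-Treat (ITT) analysis according to the arm they were randomised to". Elsewhere the set is narrower:

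- SAP 1.2 places mRNA vaccination after allocation: "Subsequent to randomization to either MMR or placebo injection, a number of participants in the CROWN CORONATION trial were vaccinated".
- SAP 1.3 compares MMR followed by SARS-CoV-2 vaccination with "recent placebo injection followed by SARS-CoV-2 vaccination".
- SAP 2.1 says that, at one site, "consenting participants are recruited into the sub-study".
- SAP 2.4 gives the ceiling: "The eligible population size is 160".
- SAP 2.5 times the blood draw from the second mRNA dose.

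**The concern.** Of the four sensitivity terms, age is the only one settled before randomisation. The three intervals depend on vaccination or sampling dates that come later, so there is good reason to keep them out of the main model. That reason does not apply to age.

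The result to be reported is the adjusted arm difference with its 95% CI, so the precision of the main model is what readers will see. Recruitment is capped at 160 eligible people. Complete-case analysis and the RPMI exclusion can shrink each endpoint further. Adjusting for a prognostic baseline variable is one of the few remaining ways to gain precision, and age is already planned for use, at least for the primary endpoints.

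The wording in 3.1 is a smaller, separate matter. Read literally, it describes everyone randomised in the parent trial, which is not the set analysed here.

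**Working it through.** **Inputs from SAP 2.4.** Two-sided 5% t-test; SD 900; difference 400 pg/ml (TLR-3 ligand) or 450 pg/ml (TLR-7/8 ligand); N = 60, 100, 140. The allocation ratio is not stated. Equal arms are assumed.

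**Step 1: reproduce Table 1.** SE = 900 × √(4/N), which is 232.4, 180.0 and 152.1 pg/ml. Power comes from the noncentral t distribution with N−2 degrees of freedom and noncentrality difference/SE (for TLR-3: 1.72, 2.22, 2.63).

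| | N=60 | N=100 | N=140 |
|---|---|---|---|
| TLR-3, recomputed (stated) | 39.5% (39%) | 59.5% (59%) | 74.2% (74%) |
| TLR-7/8, recomputed (stated) | 47.8% (48%) | 69.7% (70%) | 83.6% (84%) |

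Table 1 reproduces with equal arms.

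**Step 2: the two models.** Arm, sex and three quarter terms plus the intercept make 6 parameters, so the main model has N−6 degrees of freedom; with age it has N−7. This assumes that all four quarters occur. For the age model

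SE = 900 × √(1−R²) × √(4/N) / √(1−r²)

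where R² is the share of variance left after sex and quarter that age explains, and r² is the chance squared correlation of age with arm. Power is averaged over r² ~ Beta(1/2, (N−2)/2). The SAP gives no R², so 0-10% is an assumption. Table 1's 900 is taken as the residual SD.

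| Power | Main model | + age, R²=0 | R²=5% | R²=10% |
|---|---|---|---|---|
| TLR-3, N=60 | 39.4% | 38.8% | 40.5% | 42.3% |
| TLR-3, N=100 | 59.5% | 59.0% | 61.2% | 63.6% |
| TLR-3, N=140 | 74.2% | 73.9% | 76.1% | 78.3% |
| TLR-7/8, N=60 | 47.7% | 47.0% | 49.0% | 51.1% |
| TLR-7/8, N=140 | 83.6% | 83.3% | 85.1% | 87.0% |

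The loss at R²=0 is largest for TLR-7/8 at N=60 (47.7 − 47.0 = 0.7 points) and smallest at N=140 (about 0.3 points).

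**Step 3: break-even.** The two models have equal power when R² is 1.8% (N=60), 1.0% (N=100) or 0.7% (N=140).

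**Step 4: interval width.** The average 95% CI half-width at N=60 goes from 466 pg/ml to 470 (R²=0) or 446 (R²=10%). At N=140 it goes from 301 to 302 or 287.

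**Step 5: check.** Step 2 charges chance imbalance to age only. If each model is averaged over chance correlation with all its own covariates, TLR-3 power, main versus age at R² = 0 and 10%, is 37.2% versus 36.6% and 39.9% (N=60), and 73.0% versus 72.7% and 77.1% (N=140). The levels are 1-2 points lower, the change due to age is about the same, and break-even is 1.9%, 1.1% and 0.8%.

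**Analysis set.** No arithmetic applies. SAP 3.1 speaks of all randomised participants. SAP 1.2, 2.1, 2.4 and 2.5 require mRNA vaccination after randomisation, consent and a blood sample. SAP 3.2 refers to all participants in the sub-study, which is the accurate description.

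**The case against.** The strongest reply is that nothing here is wrong. SAP 3.3.1 to 3.3.3 agree on the main covariates, the age-adjusted primary estimates will be produced anyway, and SAP 3 calls the work hypothesis generating, so no decision rests on which model is labelled main. All of this stands, and it is why the point is an optional improvement.

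The size is also modest and its basis narrow. Even at 10%, N=60 remains underpowered. The figures cover only the two IFN-γ comparisons in Table 1; nothing is computed for the other cytokines, neutralisation or measles IgG. This stands too.

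For the secondary endpoints, planned use of age is less clear: 3.3.1 opens with models for the primary outcomes, and 3.3.3 does not mention age. Including it there would therefore be a small extension.

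A reader might infer that adding age is certain to gain precision. The SAP does not support that, because it gives no age-outcome association, and below break-even there is a small loss. A reader might also infer that the present estimate is biased. Nothing in the document shows this: the model is valid and prespecified.

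On the set, a reader might infer that 3.1 conceals selection after randomisation. It does not: 3.1 itself says the analysis is the main strategy for the sub-study, and the other sections state vaccination, consent and sampling openly.

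**Conclusion.** The plan is not in error, but a cheap improvement is available. Age in the main model helps if it explains more than about 2% of the residual variance at N=60, or about 1% at N=100 to 140. Under the assumed 0-10%, the change in TLR-3 power runs from a loss of about 0.6 points to a gain of about 3 (N=60), from a loss of 0.4 to a gain of 4 (N=100), and from a loss of 0.3 to a gain of 4 (N=140). Across both Table 1 stimuli the worst loss is 0.7 points. The downside is bounded and smaller than the plausible upside.

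This rests on equal arms, 900 as the residual SD after sex and quarter, four observed quarters, a linear age term and the assumed range for R².

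The 3.1 wording is a minor clarification that would not merit a point by itself. Analysis by randomised arm is clear, and no size or direction of bias is claimed.

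**What to change.** - **Main model (SAP 3.3.1 to 3.3.3).** Use arm + sex + quarter of sampling + age (continuous) for primary and secondary endpoints. Settle this before any comparison by arm is seen.
- **Sensitivity analyses (SAP 3.3.1).** Keep the sex-and-quarter model as the sensitivity analysis that replaces the age one. State that each of the three interval durations is added individually to the new main model; otherwise their base model is undefined.
- **Analysis set (SAP 3.1).** Replace the opening with wording such as: *Data from all sub-study participants with an evaluable endpoint will be included*. Keep the existing clause on analysis by randomised arm. Add that entry to the sub-study (mRNA vaccination, consent, sampling) occurs after randomisation.

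**Cost.** SAP wording and one degree of freedom. If age explains nothing, about 0.3-0.7 points of power are lost. No new data are needed, since the SAP already plans to use age.

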### 3.3.2 Primary endpoints analysis

TNF- $\alpha$ , IL-1 $\beta$ , IL-6, IL-10, IL-17, IL-22, IFN- $\alpha$  and IFN- $\gamma$  will be analysed by linear regression, with a coefficient for treatment arm, and adjusted for sex and the calendar date (which quarter of the year) of sample collection. The endpoints will be reported as the adjusted mean (95% CI) effect of MMR pre-exposure on the endpoint. For each specified endpoint, the individual participant assay response to RPMI will be evaluated and if the response is greater than three times the lower detectable limit of the assay, the data from that participant will be excluded from analysis for the specific endpoint. For example, if the IL-6 value is greater than three times the lower detectable limit in response to RPMI, the participant's data will be excluded from the analyses of IL-6 responses to the heterologous stimuli. The participant's data will still be used for the other endpoints in which the assay response to RPMI was less than three times the lower detectable limit.

### 3.3.3 Secondary endpoints analysis

SARS-CoV-2 neutralization assay (EC50; IC50) and Measles IgG antibody titres will be analysed by linear regression, with a coefficient for treatment arm, and adjusted for sex and the calendar date (which quarter of the year) of sample collection.

## 5 REVISION HISTORY
